3.0 STUDY OBJECTIVES/ENDPOINTS

3.1 Primary Objective

Determine feasibility and acceptability of study methods and examine changes in pre- and post-treatment measures of function, patients' self-report of symptoms and QOL, and patients and caregivers' post self-report of readiness for discharge. We will include 10 control and 10 intervention patients.

Feasibility: We plan enrollment of 60% of those approached; achieve 75% retention rate, 75% of intended data collection; and no intervention-related adverse events. The PACT intervention team will have a reduced workload; we will record effort required to deliver the PACT intervention. These feasibility data will inform if, or to what extent, workload is affected to plan future studies and implementation. The team will receive 32 hours of training in palliative care and adaptive leadership approaches. Adherence will be monitored by electronic tracking from OT and PT notes and by self-report.

Acceptability: Assessed by interviews and surveys with patients and their caregivers about their experiences.

Changes in pre-and-post QOL, symptoms, and function: Compare changes between control and intervention.

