3.4 Primary Endpoint

3.4.1 Feasibility will be defined as: % approached, retention rate (% of consented patients who completed the intervention); % intended data collection, safety (# of adverse events).

3.4.2 Adherence will be monitored by electronic tracking from OT and PT notes and by self-report during the intervention.

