5.3.2 PRO-CTCAE (daily measures)

This 78-item measure, developed at the National Cancer Institute (NCI) allows patients to self-report symptom-based adverse events. We will use a subset of 19 symptoms to assess symptom attributes (e.g., presence, frequency, severity, interference with symptom) deemed relevant for cancer patients; these symptom-items have been extensively evaluated by cancer patients using cognitive interview³² methods and found to be clear, comprehensible, and capable of measuring the symptoms of interest and are most relevant for this population, such as nausea and vomiting. In our bone marrow transplant study (preliminary study 3, in which most of the patients had some type of leukemia, these items captured symptoms of fatigue, diarrhea, heartburn, nausea, appetite, anxiety, mouth sores, vomiting, pain, constipation, sadness, cheering-up, insomnia, cough, rash, and shortness of breath. In the proposed study, both the control and intervention groups will be asked to answer the 19 questions daily to capture changes over time. Recent data have shown that daily collection of patient-reported symptoms is feasible and acceptable to bone marrow transplant patients in the inpatient setting, who are often patients with AML.³³ We will calculate a total symptom score. This symptom score represents treatment-related symptom burden for that patient on that particular day.

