10.2 Sample Size and Accrual

Sample size for this study is mainly determined by time and resource (budget) constraints. We will allocate 26 patients to the two groups (12 per group). We assume 20% of values will be missing or otherwise unusable, yielding complete data for 10 patients per group for analyses. As stated

above, estimation rather than statistical inference is our focus, and so it is not this project's goal to have adequate statistical power. We can focus instead on precision, and for the primary outcome of QOL (standardized), the half-width of a two-sided 95% confidence interval would be .9SD, assuming 10 patients per randomized group. We obtained this result using nQuery Advisor v7.0 software.

We claim such a study as feasible if and only if both (a) recruitment rate (p) is high enough and (b) retention rate (q) is sufficiently high, i.e., if both p and q are large enough. More specifically, this is to test the following hypothesis:

$$H_0: p \leq 50\% \text{ or } q \leq 50\% \text{ vs } H_1: p \geq 80\% \text{ and } q \geq 70\%.$$

Denote N as the number of eligible patients we try to recruit, and Y as the number of patients who are recruited, X as the number of patients (among the Y who are enrolled) who complete the PACT intervention. The target value of Y is 20, and we assume (1) N follows a negative binomial distribution, $NB(20, p)$, (2) X , conditional on ($Y = 20$), follows a binomial distribution $B(20, q)$. We further assume that N and X are independent. We list cut-offs and associated type I error and power under different N and X values for rejecting the hypothesis of $p \leq 50\%$ and the hypothesis of $q \leq 50\%$.

Recruitment (N: total number of patients being approached)

Y	Rejection Area	Type I error ($p \leq 50\%$)	Power ($p \geq 0.80$)
20	$N \leq 20+12$	0.108	0.994
20	$N \leq 20+13$	0.148	0.997
20	$N \leq 20+14$	0.196	0.999
20	$N \leq 20+15$	0.250	0.999

Retention (X: total number of patients who complete the intervention)

Y	Rejection Area	Type I error ($q \leq 50\%$)	Power ($q \geq 0.70$)
20	$X > 8$	0.748	0.995
20	$X > 9$	0.588	0.983
20	$X > 10$	0.412	0.952
20	$X > 11$	0.252	0.887

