10.3 Data Analysis Plans

Feasibility Data Management and Analysis

Data will be collected on feasibility metrics. These include collecting and recording data on all patients approached for recruitment, along with an indicator of whether each patient is enrolled or not. The proportion of those enrolling, along with its 95% confidence interval, will be

computed. Of those enrolled, we will record whether there is attrition prior to each patient's end of follow-up, as well as the reasons for such attrition. The proportion of those retained, along with its 95% confidence interval, will be computed as 1 minus the proportion who experienced attrition from the study. The frequency of data values will also be tracked, and the proportion of non-missing data values, along with its 95% confidence interval, will be computed. The frequency and type of adverse events, including intervention-related adverse events, will be recorded. Staff hours reflecting the effort required to deliver the intervention to each patient enrolled into the intervention arm will be tracked; its mean and standard deviation will be computed across patients.

Acceptability Data Management and Analysis

Interviews will be transcribed by a professional transcription agency. Using Atlas.ti for analysis, Drs. [name] and [name] will read transcripts to derive codes. They will review and discuss labels to group codes into related categories and identify major themes through this process. After we define each major theme, we will identify corresponding exemplar quotes. We will address trustworthiness of analysis procedures and findings through creation of an audit trail to record data collection, coding, and analysis decisions. The interviewer ([name]) will make reflexive memos after each interview and review memos with corresponding audio recordings to discern linkages, gaps, and questions. When the two coders do not agree on their initial code, code negotiation and transcript review will occur.

Analysis of Change in Pre-and-Post QOL, Symptom, and Function

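### The 95% interval for data completeness counts values, with no allowance for their clustering within about 20 patients; a simple binomial interval would be too narrow

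*Combined protocol and SAP*

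**What the plan says.** The feasibility part of Section 10.3 reports three proportions, each "along with its 95% confidence interval". The first two, enrolment and retention, count patients. The third counts something else: "the proportion of non-missing data values, along with its 95% confidence interval, will be computed". The section gives no interval method, no denominator and no adjustment for repeated values from one patient. Staff hours, in the same paragraph, are explicitly summarised across patients. Within-patient correlation is mentioned only later in 10.3, for the repeated-measures models of the outcomes.

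The target is in Section 3.1: "achieve 75% retention rate, 75% of intended data collection". Section 3.4.1 lists the percentage of intended data collection among the primary feasibility measures, again without a denominator.

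On the volume of data, Section 5.3.2 says that "both the control and intervention groups will be asked to answer the 19 questions daily to capture changes over time", and Table 5 (Section 8.0) shows symptom collection in both groups over about days 1 to 60. Other places are narrower. Section 2.0 ties the nurse's daily symptom assessment to hospitalization. Table 1 (Section 1.5) has daily nurse monitoring on days 1-7 and 31-37, with calls twice a week in between. Table 5 lists twice-weekly post-discharge assessments for the intervention group only.

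On the number of patients, Section 10.2 states: "The target value of Y is 20". The same section also mentions 26 patients and 12 per group. Its feasibility rule uses recruitment and retention only.

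**The concern.** Values from one patient are not independent. A patient who becomes too ill, withdraws or dies loses a long run of forms, and Section 9.4 removes patients who cannot complete the activity because of complications. The information about completeness therefore comes mainly from the number of patients, not the number of entries. A binomial interval over pooled entries would treat 20 x 60 = 1,200 forms, or 20 x 1,140 = 22,800 item values, as that many independent observations.

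At stake is one of the primary feasibility measures, with a numeric target, in a study that says its focus is estimation and precision. A report could show an interval lying wholly above or below 75% when the data cannot support that.

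**Working it through.** **The plan's own figure.** The documents give no half-width or sample size for the completeness interval, so there is nothing to reproduce directly. The one precision figure in Section 10.2, a half-width of .9 SD for QOL, does reproduce with the patient as the unit: 1.96 x sqrt(2/10) = 0.88 SD.

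**Inputs from the documents.** K = 20 patients (10.2); target 75% (3.1); 19 items per day (5.3.2); about 60 days (Table 5), or 14 days if daily collection is limited to days 1-7 and 31-37 (Table 1).

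**Assumptions.** The ICC of missingness is not given; 0.01 to 0.5 is shown. The number of values per patient, m, is taken as 60 forms, 14 forms, 19 x 60 = 1,140 items, or about 10 assessments.

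**Formulas.**
- Simple binomial half-width = 1.96 x sqrt(p(1-p)/(K m)).
- Design effect DE = 1 + (m-1) x ICC; clustered half-width = simple half-width x sqrt(DE).

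Example, m = 60, p = 0.75: simple = 1.96 x sqrt(0.1875/1,200) = 2.45 points. At ICC 0.1, DE = 1 + 59 x 0.1 = 6.9, sqrt = 2.63, half-width 6.4 points.

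| Values per patient | Simple | ICC 0.01 | 0.05 | 0.10 | 0.30 | 0.50 | Ratio at ICC 0.1-0.5 |
|---|---|---|---|---|---|---|---|
| 60 daily forms | 2.45 | 3.1 | 4.9 | 6.4 | 10.6 | 13.5 | 2.6-5.5 |
| 14 daily forms | 5.1 | 5.4 | 6.5 | 7.7 | 11.2 | 13.9 | 1.5-2.7 |
| 1,140 items | 0.56 | 2.0 | 4.3 | 6.0 | 10.4 | 13.4 | 10.7-23.9 |
| about 10 assessments | 6.0 | 6.3 | 7.2 | 8.3 | 11.5 | 14.1 | 1.4-2.35 |

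(Half-widths in percentage points.) The ratio does not depend on K, so the choice between 20, 24 and 26 patients does not alter it. For 60 forms it reaches 2 when DE = 4, that is at ICC = 3/59 = 0.05.

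**What ICC is plausible?** Suppose dropout is the only difference between patients, dropout times are uniform over follow-up, values after dropout stay in the denominator, and overall completeness is 75%. With retention R, the completion rate while in the study is r = 0.75/(R + (1-R)/2), the between-patient variance is r^2 (R + (1-R)/3) - 0.75^2, and the ICC is that variance divided by 0.1875.
- R = 0.75 (the 3.1 target): r = 0.857, variance 0.0497, ICC 0.27. The patient-level half-width is 2.093 x sqrt(0.0497/20) = 10.4 points.
- R = 0.70 (the 10.2 alternative): ICC 0.32.
- R = 0.90: ICC 0.10. R = 0.95: ICC 0.05.

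**Coverage under the same dropout model (simulation, 20 patients).** At 75% retention the simple 95% interval covers 36% of the time for 60 forms and 9% for items; a t-interval on patient proportions covers about 91% and 90%. At 90% retention the simple interval covers 52% and 14%, the t-interval 82% and 77%.

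**Effect on a statement about 75%.** With 80% observed on 60 forms, the simple half-width is 1.96 x sqrt(0.16/1,200) = 2.26 points.
- Simple: 77.7-82.3%, excludes 75%.
- ICC 0.05: 75.5-84.5%, still excludes 75%.
- ICC 0.10: 74.1-85.9%, includes 75%.
- ICC 0.27: 70.7-89.3%, includes 75%.

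**The case against.** A reader might infer that the plan prescribes a binomial interval and that the interval is therefore several-fold too narrow as a matter of fact. The documents do not support that. Section 10.3 names no method, and a cluster-robust or bootstrap interval is compatible with the same sentence. The factor rests on an assumed ICC and an assumed number of values. Sections 2.0, 1.5 and 8.0 leave open whether daily forms run for 60 days or far fewer. This objection stands, and it is why the size is given only as a conditional range.

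A second objection is that completeness may be meant per measure and time point, with one value per patient and so no within-patient clustering; the half-width would then be 1.96 x sqrt(0.1875/20) = 19 points. Section 10.2 does move from 20% missing values to 10 usable patients per group (12 x 0.8 = 9.6), which treats values much like patients. But 10.3 describes a single overall proportion of values, so this is not the natural reading of the sentence.

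Third, the consequence is limited. The rule in 10.2 declares feasibility from recruitment and retention alone, and nothing compares the completeness interval with 75%. The choice of interval does not bias the point estimate. This stands.

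Finally, the remedy is imperfect: the denominator has to be settled first, and patient-level intervals can under-cover with about 20 patients. Both are true. They affect how the fix is written; the simple interval remains much worse.

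**Conclusion.** The point holds as a gap in a primary feasibility measure: the plan counts values, makes no allowance for clustering within about 20 patients, and the ordinary way of carrying out the sentence gives an interval that is too narrow for any positive ICC. At an ICC of 0.1 to 0.5 the shortfall is substantial for a long run of daily forms and very large for item-level counting. With few forms per patient or a small ICC it is modest. The dropout model makes 0.1 to 0.5 reasonable at the retention the plan expects, but only if values after dropout remain in the denominator, which the plan does not say.

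It would be wrong to infer that the feasibility decision is compromised. Completeness lies outside that rule, so the damage is confined to a misleading precision statement about the 75% target.

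**What to change.** In Section 10.3:
- Define the denominator: which measures, forms and days are intended in each group, whether a form or an item is the value, and whether values scheduled after death or withdrawal count as intended. The differing descriptions of symptom collection in Sections 1.5, 2.0, 5.3.2 and 8.0 need to be reconciled for this.
- State that the interval takes the patient as the unit. For the pooled proportion, use a patient-level bootstrap or a cluster-robust interval. Alternatively, report the mean of per-patient completion proportions with a t-interval. These are different quantities if patients have different numbers of intended forms, so name the one chosen.
- If results are also given by group, note that each interval then rests on about 10 patients.

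No new data are needed. The cost is a short addition to 10.3 and a wider reported interval, which may still cover somewhat less than 95% with about 20 patients.

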2.0 STUDY PURPOSE AND DESIGN

This is a single institution, feasibility trial of 20 (10 control and 10 intervention) patients with the primary objective of assessing feasibility, acceptability, and change in pre and post measures of symptoms, function, and QOL by administering the PACT intervention.

Study subjects will be identified by the Study Coordinator through pre-screening through the electronic health record after being referred by the oncologists and pharmacists. Eligible patients will be approached by the Study Coordinator to confirm eligibility, which includes requesting permission of the patient's attending physician. Seven days prior to and within three days after initiation 1st cycle HMA or low-dose cytarabine + VENE, written informed consent will be obtained (A total of 10 days of recruitment period and baseline assessment).

First, ten participants in the control group will receive usual care. After the control patients have completed the study, then 10 intervention participants will receive the PACT intervention, a novel symptom management intervention, which aims to build patient skills to manage AML treatment-related, and chronic illness symptoms. Because patients receive chemotherapy during the first 7 days of hospitalization or clinic visit, the intervention will start at day 1 or day 2 of chemotherapy. During hospitalization, the PACT RN will assess AML symptoms daily (using PRO-CTCAE), and PACT OT and PT will assess function at baseline (day 1 or 2), days 3 or 4, and days 6 or 7. This study uses UNC hired staff of RNs, OTs, and PTs to deliver the intervention.

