The first 10 patients will be assigned to the control group. All patients (assigned to either intervention or control groups) will undergo the exact same battery of quality of life, symptom, and functional measures at baseline (prior to beginning the intervention), and throughout different time points throughout the study (see Data Collection Procedures/timeline below). Once consent is provided, study personnel may contact enrolled participants up to 2 years from their acute leukemia diagnosis. All patients cluster randomized into the intervention group will receive standard care plus the PACT intervention for the duration of the study.

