5.3 Description of Assessments and Questionnaires

Assessment Tool	Discipline	Indication
European Organization for Research and Treatment of Cancer QLQ-C30	PI or Research Assistant	Self-report QOL: functional scale & symptom scale
PRO version of the Common Terminology for Adverse Events (PRO-CTCAE)	PI or PACT RN	19 items** (diarrhea, chills, heartburn, nausea, appetite, mouth sores, vomiting, constipation, cough, rash, shortness of breath, fatigue, anxiety, sadness, nothing will cheer me up, pain, insomnia, concentration, and memory)
Activity Measure in Post-Acute Care (AM-PAC)	OT & PT	Guides discharge planning; guides resource utilization; provides insight re: patient mobility
Karnofsky Performance Scale (KPS)	PI or Research Assistant	Classified participants' functional impairment
Possibilities for activity Scale (PACTS)	PI or Research Assistant	Assessing self-efficacy and motivation of performing meaningful activity

Timed Up and Go~10 feet (3 meters)	PT	Assesses patient mobility, balance and fall risk
BERG Balance	PT	Falls Risk
Muscle Strength	OT	Prognostic & Predictive Marker, Handheld Dynamometry
Modified Canadian Occupational Performance Measure (COPM)	OT	Self-care, leisure, and productivity outcomes; goal attainment scale
Performance Assessment of Self-care Skills (PASS)	OT	Ability to perform daily tasks
Clock Drawing	OT	Assess cognitive abilities
Demographics and Clinical Characteristics	PI or Research Assistant	Demographic: date of birth/age, sex, race/ethnicity, insurance, education, income, marital/partner status, number of people in the household, employment status, insurance type, falls in last 6 months Clinical: type of acute leukemia, white blood cell, hemoglobin, hematocrit, platelets, lactate dehydrogenase, neutrophil count, cytogenetics and blast percentage, height and weight, comorbidity, and treatment type(s)
Care Transitions Measure (CTM)	PI or Research Assistant	Assesses readiness for discharge
Patient Activation Measure (PAM)	PI or Research Assistant	Assesses self-management
Preparedness for Caregiving Scale FACT-Leu Additional Concern subscale	PI or Research Assistant PI or Research Assistant	Assesses preparedness for caregiving Assess disease burden

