8.0 TIME AND EVENTS TABLE

Table 5. Measures

Variable Measured	Measure Description and Reliability	Baseline cycles 1 & 2 (7 days prior or within 3 days of infusion initiation)	Symptom and QOL BOTH GROUPS (About days 1-60)	HMA or low-dose cytarabine completion at cycle 1 & 2 (within 2 days or up to 7 days after the end of infusion)	Post-discharge, 2x week assessments Monday & Thursday INTERVENTION ONLY days 8-30	Before cycle 4 (About day 90)	Data Collector
Demographic and clinical variables	Age, sex, race/ethnicity, insurance, education, income, employment status, marital/partner status, number of people in the household. Treatment type, comorbidities, remission status, blood test results, height and weight.	X			Continuously monitor clinical characteristic, ex: blood result, remission status		Research Assistant
Health Care Utilization	Number and reasons for: emergency department visits, rehospitalizations Length of hospital			Electronic chart abstraction and self-report			Research Assistant
Quality of Life							
QOL	EORTC QLQ-C30 ³⁰ , $\alpha = .89$ (5 functional scales, global health status/QOL scale, cognition, financial impact)	X	X (baseline of cycle 3)			X	Research Assistant
Symptoms							
AML symptoms	PRO-CTCAE 19 items ⁴² (diarrhea, chills, heartburn, nausea, appetite, mouth sores, vomiting, constipation, cough, rash, shortness of breath, fatigue, anxiety, sadness*, nothing will cheer me up, pain, insomnia, concentration, and memory)	X	X	X	X	X	PACT RN
Disease burden	FACT-Leu Additional Concern subscale	X				X	Research Assistant
Function							
Participation in Meaningful Activity	Possibilities for Activity Scale (PActS) ³⁴ - 12 items stratified $\alpha = .77$ – internal consistency .91 - .89	X				X	Research Assistant
Performance Status	Clinician reported Karnofsky Performance Scale ³⁷ - 1 item for clinician; $r = .89$	X		X		X	Research Assistant
Self-care	PASS- Performance Rate Assessment of Self-Care Skills	X					PACT OT
Grip Strength	Hand grip strength	X					PACT OT
Balance	Berg balance test	X					PACT PT
Mobility	Timed Up and Go (3 meter)	X					PACT PT
Function	Activity Measure for Post-Acute Care (AM-PAC) "6 clicks" - 6 items for OT; 6 items for PT; $\alpha = .92 - .94$	X					PACT OT and PT
Cognition abilities	Clock Drawing Assessment	X					PACT OT
Readiness for Discharge and Self-Management							
Readiness for Discharge	Care Transitions Measure ⁴³ , 15 items, $\alpha = .93$			X			PACT RN

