Analyses will be conducted following an intention to treat approach, such that patients are analyzed as allocated. Descriptive statistics will be computed on all analysis variables at each time point separately for each condition. These values will be compared between the conditions at baseline to determine whether any imbalanced. These include means and standard deviations for continuous variables, and frequencies and percentages for categorical variables. As the primary analysis of pre and post values, we will fit an analysis of covariance (ANCOVA) model for each post outcome, with a main effect for group (intervention versus control) while controlling for the covariate of the corresponding baseline (pre) value. Sensitivity analyses will repeat this ANCOVA but adding demographic variables that are imbalanced at baseline, subject to sufficient sample size. This approach will allow us to assess whether the mean post values differ between groups for each measure through the regression coefficient for the main effect of group, as well as its 95% confidence interval. This information will be useful in planning for the subsequent R01, and we will calculate effect sizes for the post measure as the ratio of the mean difference between the intervention and the control groups to its standard deviation. For measures where more than one follow-up measure is collected, this approach can be extended through a linear mixed effects model approach to repeated measures analysis, and within-patient correlation can be estimated. If extensive (e.g., greater than 10%), multiple imputation will be considered for missing values. No formal significance testing will occur, as the intention is to evaluate and estimate effect sizes rather than formal hypothesis testing, and hence multiplicity is not a concern from this perspective.

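### The sensitivity ANCOVA can add only demographic covariates, so the plan will not show how far a clinical imbalance between sequentially filled groups moves the group effect

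*Combined protocol and SAP*

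**What the plan says.** Allocation follows enrolment order. Section 2.0 states: "First, ten participants in the control group will receive usual care", and then "After the control patients have completed the study, then 10 intervention participants will receive the PACT intervention". Section 5.1 agrees: "The first 10 patients will be assigned to the control group". The same section also says "All patients cluster randomized into the intervention group will receive standard care plus the PACT intervention", but no randomization procedure is described anywhere.

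Section 10.3 compares descriptive statistics on the analysis variables between conditions at baseline. The primary model for each post value is an ANCOVA with a group effect "while controlling for the covariate of the corresponding baseline (pre) value". Sensitivity analyses repeat it "adding demographic variables that are imbalanced at baseline, subject to sufficient sample size". The group coefficient, its 95% confidence interval and a standardized effect size are intended for planning the R01, with no formal testing.

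The clinical baselines exist. Section 5.3 has a demographic list and a separate clinical one, which opens "Clinical: type of acute leukemia, white blood cell, hemoglobin" and ends with comorbidity and treatment type. The Section 8.0 table marks "Treatment type, comorbidities, remission status, blood test results, height and weight" for collection at baseline. It also marks clinician-rated KPS at baseline, filed under function. Section 5.3.3 says that lower KPS goes with worse survival in most serious illnesses.

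**The concern.** The two groups are recruited in different periods, and the open group is known when each patient is referred and judged fit. Section 4.1 sets no performance-status limit. Section 4.2 excludes patients whose oncology provider considers them unable to take part, and Section 9.2 has the attending oncologist confirm eligibility. That judgement could differ between a usual-care period and an activity-intervention period. If it did, the difference would be expected in performance status and comorbidity. Either chemotherapy backbone is allowed, and enrolment is planned over two years, so the treatment mix could also change.

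Because Section 5.3 keeps demographic and clinical variables apart, *demographic* in Section 10.3 does not naturally cover KPS, treatment type or comorbidity. The sensitivity model therefore cannot take up the variables most directly tied to that judgement of fitness. At stake is the effect size carried into the R01. In a study meant for estimation, bias in the estimate is the relevant harm.

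**Working it through.** **1. The plan's own precision figure (Section 10.2).** Inputs: 10 per group, two-sided 95% interval, standardized QOL. Half-width = critical value × √(1/10 + 1/10).
- Normal: 1.960 × 0.447 = 0.877 SD.
- t, 18 df: 2.101 × 0.447 = 0.940 SD.

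Both round to the stated 0.9 SD.

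**2. Possible shift in the group coefficient.** If a covariate left out of the model has standardized partial slope b, given the outcome's own baseline, and the groups still differ on it by d SD after that adjustment, the group effect shifts by b × d. The documents give neither quantity, so both ranges are assumptions.

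| b | d = 0.25 | d = 0.5 | d = 1.0 |
|---|---|---|---|
| 0.2 | 0.05 | 0.10 | 0.20 |
| 0.3 | 0.075 | 0.15 | 0.30 |
| 0.5 | 0.125 | 0.25 | 0.50 |

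The range is 0.05 to 0.50 SD. The top is 0.50/0.9 = 56% of the stated half-width.

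**3. What chance alone would do.** With 10 per group and random allocation, a standardized covariate difference has SD √0.2 = 0.447.
- P(|d| ≥ 0.5) = 2 × (1 − Φ(0.5/0.447)) = 0.264.
- P(|d| ≥ 1.0) = 2 × (1 − Φ(2.236)) = 0.025.

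These are reference values under randomization. They do not estimate drift from sequential filling, for which the documents give no figure.

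**4. Cost of one added covariate (20 patients, 10 per group).**
- Degrees of freedom go from 17 to 16, so the t multiplier goes from 2.110 to 2.120.
- If the covariate explains nothing and the groups differ by d within-group SDs, the variance factor for the group effect goes from 0.2 to about 0.2 + d²/20 (d²/18 with the sample SD). The SE ratio is √(1 + d²/4). At d = 0.5 it is √1.0625 = 1.03. At d = 1 it is √1.25 = 1.12 (1.13 with 18).
- Averaged over chance imbalance of normal covariates, the half-width is t × √0.2 × √(1 + k/(17 − k)), where k counts all covariates. Outcome baseline only (k = 1): 0.97 SD. Plus KPS (k = 2): 1.01 SD. KPS pays for itself if it explains about 1 − (0.973/1.009)² = 7% of the variance left after the outcome's baseline.
- With KPS, treatment type and comorbidity together, one term each (k = 4), the half-width is 1.10 SD on 14 df. This is why covariates should go in one at a time.

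**The case against.** Several stronger readings are tempting, and the documents do not support them.

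- **A reader might infer that a clinical imbalance would go unnoticed.** Section 10.3 compares the analysis variables between conditions at baseline, and KPS is a listed function measure, so a KPS imbalance would be displayed. Whether treatment type and comorbidity count as analysis variables is unclear, but they are not excluded from that comparison. The gap is in adjustment.
- **A reader might infer that any imbalance passes in full into the group coefficient.** The primary model already conditions on the outcome's own baseline. Sicker patients would usually differ there too, so only the remainder can bias the estimate. When KPS is the outcome, its baseline is already in the model.
- **A reader might take the 26% as the risk created by sequential filling.** It is chance imbalance under random allocation. The plan has one site and one set of criteria, and nothing in it shows drift.
- **A reader might infer that clinical variables matter more than demographic ones.** The documents call only KPS prognostic, and for survival. The demographic list includes age and recent falls, which plausibly relate to function.
- **A reader might expect adjustment to repair the sequential design.** Calendar period coincides with group, and no covariate removes it.

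It is also fair to say that the primary endpoint is feasibility, that the outcome analysis is estimation only, and that the sensitivity model already carries a sample-size caveat. That limits the importance of the point. It does not explain why a check on a non-randomized comparison should stop at demographics. The randomization wording in Sections 5.1 and 10.2 offers no defence either, because it conflicts with the sequential assignment described in Sections 2.0 and 5.1.

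**Conclusion.** The concern holds in a limited form. Beyond the outcome's own baseline, Section 10.3 allows adjustment only for imbalanced demographic variables. Clinical baselines that are already collected are therefore not eligible, although the groups are filled in sequence. An imbalance in them may be visible, but its effect on the group coefficient and on the R01 effect size would not be reported.

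The plausible shift is about 0.05 to 0.5 SD, all of it inside the stated 0.9 SD half-width. That range rests on assumed partial slopes of 0.2 to 0.5 and residual imbalances of 0.25 to 1 SD. The prognostic role of treatment type and comorbidity is a reasonable clinical assumption that the documents do not state. The primary ANCOVA, the feasibility analysis and the sample size are unaffected. The change is worth making because the data are already in hand and the cost is small.

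**What to change.** In Section 10.3:

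1. Change *demographic variables* to *demographic and clinical variables* in the sentence on sensitivity analyses.
2. Prespecify baseline KPS as a single added covariate in a sensitivity ANCOVA for every outcome other than KPS, whether or not it turns out imbalanced. This avoids choosing it from the data.
3. Add treatment type (HMA versus low-dose cytarabine) or comorbidity one at a time, and only if both categories are adequately filled, with the minimum count set in advance. Otherwise report them descriptively by group. In 20 patients one backbone may be nearly empty. The comorbidity form in Appendix 13.2.12 has eight yes/no items, so a single summary must be defined first.
4. Leave the primary ANCOVA unchanged.
5. State that adjustment addresses measured case mix only, because calendar period is fully confounded with group.

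The cost is a few sentences of text. Each sensitivity model loses 1 df. If the covariate explains nothing, the SE also rises by about 3% at a 0.5 SD imbalance and about 12% at 1 SD. There will be additional tables for each outcome. The QLQ-C30 alone has 5 + 3 + 1 = 9 scales before its single items, so these are best placed in a supplement.
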